for $i=1, 2, \dots, 50$ where i indexes the clinical sites involved in the study, PCI represents an indicator for whether a subject has been randomized to the PCI arm, DM is an indicator for whether the subject has been diagnosed with diabetes at baseline, λ_1 , represents the hazard of MACCE, and λ_{0i} represents the baseline hazard of MACCE at the i^{th} clinical site. Our model allows the baseline hazard of MACCE to vary by clinical site. Our interest lies in inference about β_1 , which represents the difference in log-hazard between the treatment arms. A Wald test statistic that is a function of β_1 can then be used to assess whether the hazard ratio for the treatment arms is within the non-inferiority margin. For this purpose, we will conduct a one-sided test at the 0.025 level of significance.

Model Diagnostics: Assessing heterogeneity of hazards across levels of confounders and assessing adherence to the proportional hazards assumption

We will perform a number of tests to confirm that the assumptions in the above model are reasonable. If the number of subjects per site is too small, we will pool smaller sites so that there are at least 10 subjects per site. Then, to confirm that the hazard of MACCE does not vary by pooled site, diabetes status and gender, we will include an interaction term between pooled site, PCI and diabetes and test whether the corresponding coefficient is greater than zero using a two-sided Wald test statistic at the 0.15 level of significance. We will take a similar approach by including an interaction term between gender and PCI. If homogeneity of the hazard by a feature is rejected, the corresponding interaction term will be included in the model. The test statistic corresponding to the primary question of interest (i.e., the treatment effect) will be evaluated in the presence of the interaction term to describe the overall treatment effect. We will additionally present the hazard ratios by levels of the modifying factor.

The proportional hazards assumption will be evaluated through graphical techniques including plots of transformed survival estimates (i.e., $\log(-\log(\text{survival at time } t))$) by log-transformed time and Kaplan-Meier curves by treatment arm. Should the assumption be violated, we can relax the assumption through inclusion of an interaction term between treatment arm and log-transformed time.

Sample Size and Power Considerations¹⁷

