Recently, the EXCEL¹⁸, NOBLE¹⁹ and BEST²⁰ trials have been published. These studies demonstrate a one year MACCE rate which is in the 10% or lower range in the CABG arm, compared with the SYNTAX and FREEDOM trials which were in the 12% range. In addition, in EXCEL, a clinically acceptable non-inferiority margin for death, CVA and MI was a hazard ratio in the 1.4 range. Because of the lower event rates after CABG in more recent studies and because we will also be including revascularization as part of MACCE, the Steering Committee feels a hazard ratio of 1.65 is more appropriate for defining a clinically acceptable non-inferiority margin. We assume a 10% of subjects in the CABG arm experience MACCE, and further that patients in the PCI arm will not experience a higher rate than those in the CABG arm. We would deem an increase in event rate up to and including a 16% event rate as not clinically inferior. Thus, given a clinically irrelevant hazard ratio of 1.65, a one-sided 2.5% significance level and 90% power to reject the null hypothesis if it is false, the sample size necessary is 645 patients per group (1290 for the entire study). These calculations are based on assumptions of uniform accrual over time, no loss to follow-up, exponentially distributed death times, and a Wald test statistic. Thus, to account for patients lost to follow-up and subject withdrawal we will enroll up to 1500 patients from up to 50 medical centers.

Sensitivity Analyses

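### The site and diabetes homogeneity check is written as one three-way term, which asks the wrong question and cannot work with about three events per site

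*Combined protocol and SAP*

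**What the plan says.** All of this is in section 10, Statistics, unless another section is named.

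- **Primary model.** A Cox model stratified by center, with terms for PCI and diabetes. Non-inferiority is judged by a Wald test on the PCI coefficient.
- **Purpose of the check** (Model Diagnostics): "to confirm that the hazard of MACCE does not vary by pooled site, diabetes status and gender".
- **Pooling.** If sites are too small, "we will pool smaller sites so that there are at least 10 subjects per site".
- **Test for site and diabetes.** "we will include an interaction term between pooled site, PCI and diabetes and test whether the corresponding coefficient is greater than zero". The Wald test is to be two-sided, with 0.15 as the threshold.
- **Test for gender.** "We will take a similar approach by including an interaction term between gender and PCI".
- **Consequence.** "If homogeneity of the hazard by a feature is rejected, the corresponding interaction term will be included in the model", and the treatment effect is then assessed with that term present.
- **Size** (Sample Size and Power Considerations). On enrolment: "we will enroll up to 1500 patients from up to 50 medical centers". On the control event rate: "We assume a 10% of subjects in the CABG arm experience MACCE".

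The plan gives no degrees of freedom for the site and diabetes test, no random effect, and no fallback if the model does not fit. Diabetes also appears among the pre-specified subgroups in section 9, and section 10 (Secondary Analyses) looks at treatment effect by baseline features as hypothesis-generating work.

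**The concern.** There are two problems.

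1. **The term does not match the purpose.** A site by PCI by diabetes term measures how the PCI-by-diabetes interaction changes from site to site. It can be zero when the PCI effect differs strongly by diabetes, and zero when it differs strongly by site. The gender test in the next sentence is an ordinary two-way term with PCI, so the plan uses two-way wording where it clearly means it.
2. **The data cannot support the term.** A fixed site-specific coefficient needs events in every arm-by-diabetes cell of that site. Where a cell is empty the estimate runs to infinity and its Wald contribution shrinks towards zero.

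The check decides which terms enter the model used for the primary test. If it cannot detect site heterogeneity, a report of homogeneity says nothing about the data. Diabetes is a randomization stratum, yet on the literal reading it gets no PCI-by-diabetes test in this check.

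**Working it through.** **Inputs.** From the documents: up to 1500 patients (1290 needed), up to 50 sites, 1:1 allocation, 10% one-year MACCE in the CABG arm with PCI expected to be no worse, 16% as the highest acceptable PCI rate, margin HR 1.65, one-sided 0.025, 90% power. Assumed, because the documents do not give them: 30% diabetes (range 20 to 40%), equal site sizes, and equal event rates with and without diabetes.

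**The plan's own figure.** Events = 4(1.960 + 1.282)² / (ln 1.65)² = 167.6. Dividing by a mean rate of (10% + 16%)/2 = 13% gives 1289 patients, or 644.6 per arm, which matches the stated 645. Both 10% and 13% are therefore carried below.

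**Coefficients.** With 50 sites the three-way term has 49 coefficients. Its lower-order companions are site by PCI (49), site by diabetes (49) and PCI by diabetes (1). The total added is 49 + 49 + 1 + 49 = 148, fewer if sites are pooled.

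**Events.**

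| Patients | Rate | Events | Per site (50 sites) |
|---|---|---|---|
| 1290 | 10% | 129 | 2.6 |
| 1500 | 10% | 150 | 3.0 |
| 1290 | 13% | 168 | 3.4 |
| 1500 | 13% | 195 | 3.9 |

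The 12% in the Protocol Summary lies between these: 1500 × 0.12 / 50 = 3.6 per site. A pooled site at the 10-patient floor has 1.0 to 1.3 events.

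**Sites with an event in all four cells.** For 30 patients at 10%, expected events are 30 × 0.10 × 0.30 / 2 = 0.45 in each diabetic cell and 30 × 0.10 × 0.70 / 2 = 1.05 in each non-diabetic cell. A Poisson hand check gives (1 − e^−0.45)² × (1 − e^−1.05)² = 0.131 × 0.423 = 5.5%. Simulation of 200,000 sites per setting gives:

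| Site size | 10% rate | 13% rate |
|---|---|---|
| 10 (floor) | 0.2% | 0.4% |
| 26 | 4.1% | 8.6% |
| 30 | 6.1% | 12.2% |

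For 26 to 30 patients the range over 20 to 40% diabetes and both rates is 2.5 to 15.5%. At 30 patients per site, about 3 of 50 sites (6 at 13%) could give a finite coefficient.

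**Reading the term as PCI by site.** Both arms have an event in about 55 to 77% of sites of 26 to 30 patients and 17 to 25% of 10-patient sites. The other sites add almost nothing to the Wald statistic, yet the reference distribution still has 49 degrees of freedom (critical value 59.2 at 0.15).

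**Behaviour of the test.** 300 trials per setting, 50 sites of 30, joint Wald test at 0.15, where 15% rejection is nominal under homogeneity:

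- Three-way term, 10% rate: 0 of 300 under homogeneity, and 0 of 300 with a between-site SD of 1.0 in the three-way log hazard ratio.
- PCI by site, 10% rate: 0 of 300 under homogeneity, and 0 of 300 with a between-site SD of 1.0 in the log hazard ratio. At 13%: 0 of 300 under homogeneity and 0 of 300 with SD 0.7.
- Three-way term with the singular matrix handled by a pseudo-inverse: 11 to 14% rejections, with or without heterogeneity.

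The result depends on how the software treats singularity, not on heterogeneity.

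**PCI by diabetes as its own term.** With 150 events and 30% diabetes, SE = √(4/45 + 4/105) = 0.356. At two-sided 0.15 (z = 1.44), power for a ratio of hazard ratios of 1.65 is Φ(0.501/0.356 − 1.44) plus a negligible opposite tail, or 49%; for 2.0 it is 69%. The ratio detectable with 80% power is exp(0.356 × (1.44 + 0.84)) = 2.25. In 200 simulated trials the term was always estimable and rejected 15% of the time under homogeneity.

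**The case against.** The strongest reply is that the sentence is loose and separate two-way terms were meant. The plan speaks of rejecting homogeneity by a feature, of showing hazard ratios across levels of the modifying factor, and of the gender test as a similar approach. This is a fair reading. On it PCI by diabetes is tested and estimable, so it cannot be said that the plan certainly omits that test. The site part still fails, and a text open to two such different analyses needs rewriting.

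A reader might also infer more than the documents support:

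- **That the whole model check is invalid.** It is not. PCI by gender is an ordinary two-way test, and the proportional-hazards plots stand on their own.
- **That heterogeneity by diabetes is ignored.** It is a pre-specified subgroup in section 9. That comparison does not decide what enters the primary model, but it exists.
- **That sites have about one event.** That holds only at the pooling floor of 10 patients; the average is 2.6 to 3.9.
- **That the non-inferiority result is biased.** Nothing here shows that. If the test does not reject, the planned model and its one-sided 0.025 test stay as they are.

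Finally, the estimability problem concerns fixed site effects. A random effect or coarser grouping could be fitted, but the plan specifies neither.

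**Conclusion.** The concern holds for the site and diabetes part of the homogeneity check, and only for that part. As written, the term answers a question the plan did not ask, has up to 49 coefficients where the text names one, and could be estimated in roughly 4 to 12% of average-sized sites. Fitted with fixed site effects, the Wald test either fails or almost never rejects, so a finding of no heterogeneity would carry no information. If two-way terms were meant, the diabetes half is sound and the site half still fails.

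The conclusion rests on up to 50 roughly equal sites, event rates of 10 to 13%, and an assumed diabetes share of 20 to 40%. Larger pooled sites would ease the sparsity: at 60 patients, 29% of sites have events in all four cells (10% rate, 30% diabetes). It should be corrected because a rule that decides the content of the primary model ought to be workable, but it is not evidence against the primary test itself.

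**What to change.** Rewrite the sentence in Model Diagnostics:

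1. Delete the site by PCI by diabetes term.
2. Test PCI by diabetes as a separate 1-degree-of-freedom term, by Wald or likelihood ratio. Drop the phrase about a coefficient above zero, which sits badly with a two-sided test.
3. For site, test PCI by region (United States versus elsewhere, already a listed subgroup), or fit a random PCI-by-site effect and report its variance.
4. State that the primary non-inferiority test stays on the overall treatment effect, whatever these checks show. A working test at 0.15 will reject about 15% of the time under homogeneity. With an interaction in the model and diabetes coded 0/1, the PCI coefficient would be the effect in patients without diabetes only.

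The cost is analysis wording, with no change to data collection or sample size. Site-level fixed interactions are given up, though they could not be estimated. Power for the diabetes interaction is moderate: the ratio of hazard ratios detectable with 80% power runs from 1.95 to 2.73 over 129 to 195 events and 20 to 40% diabetes. A non-significant result should therefore not be reported as proof of homogeneity.

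### An interaction significant at 0.15 must enter the primary non-inferiority model, but the overall effect then set against HR 1.65 has no defined contrast or weights

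*Combined protocol and SAP*

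**What the plan says.** Section 10, Primary Analysis Plan, allows a log-rank test or, if appropriate, a Cox model stratified by center with diabetes as a covariate. The Cox model is introduced as an example. In it "PCI represents an indicator for whether a subject has been randomized to the PCI arm", and interest lies in β1, "which represents the difference in log-hazard between the treatment arms". A Wald statistic that is a function of β1 is the only statistic the plan links to the margin, at one-sided 0.025.

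The Model Diagnostics subsection then adds a data-dependent step:

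- Small sites are merged: "we will pool smaller sites so that there are at least 10 subjects per site".
- For a term combining pooled site, PCI and diabetes, the plan will "test whether the corresponding coefficient is greater than zero using a two-sided Wald test statistic at the 0.15 level of significance". Gender x PCI is handled in a similar way.
- The consequence is mandatory: "If homogeneity of the hazard by a feature is rejected, the corresponding interaction term will be included in the model".
- The primary test statistic "will be evaluated in the presence of the interaction term to describe the overall treatment effect".
- Subgroup results come on top: "We will additionally present the hazard ratios by levels of the modifying factor".
- For non-proportional hazards the wording is only permissive: "Should the assumption be violated, we can relax the assumption through inclusion of an interaction term between treatment arm and log-transformed time".

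The Sensitivity Analyses subsection reports the primary analysis as final. It does not say whether that means the main-effects model or the enlarged one.

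**The concern.** In the main-effects model β1 is the treatment effect, so the margin test is well defined. Once a PCI interaction is in the model there is one log hazard ratio per level, and an overall effect exists only after someone chooses how to average them. Event weights, patient-share weights and equal weights are all legitimate overall effects. The plan names none of them, and the coefficient it does name is no longer an average.

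Two analysts who both follow the text could therefore set different quantities against 1.65 in the same data and disagree on non-inferiority.

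The site gate is also incompletely specified. It speaks of a single coefficient, and it pairs a greater-than-zero question with a two-sided test. A pooled-site interaction has many coefficients: 49 for the three-way term if all 50 sites stay unpooled.

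**Working it through.** **Plan's own figure.** Events needed = 4(1.960 + 1.282)² / (ln 1.65)² = 167.6. Dividing by a mean one-year risk of 13% (10% CABG, 16% PCI) gives 1,289 patients, or 645 per group. This matches Section 10.

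**Why β1 changes meaning.** Add a binary modifier G and PCI x G with coefficient β4. The log HR is β1 at G = 0 and β1 + β4 at G = 1. An overall effect with weight w on the reference level is β1 + (1 − w)β4. Testing β1 alone means w = 1.

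**One data set, two verdicts.** Assumed: 168 events, 20% in the minority level, HRs 0.95 (majority) and 1.70 (minority).
- Variances 4/134.4 = 0.0298 and 4/33.6 = 0.1190. Interaction z = ln(1.70/0.95) / √0.1488 = 0.582/0.386 = 1.51, p = 0.13, so the term enters.
- Event weights: 0.8 ln 0.95 + 0.2 ln 1.70 = 0.065, SE √(4/168) = 0.154. HR 1.07, upper limit 1.44: non-inferior.
- Equal weights: 0.240, SE ½√0.1488 = 0.193. HR 1.27, upper limit 1.85: not shown.
- β1: upper limit 1.33 if the majority level is the reference, 3.34 if the minority level is.

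**Operating characteristics with no true interaction.**
- From the plan: margin 1.65, one-sided 0.025, gate two-sided 0.15 (|z| > 1.44), 1,500 patients, 10% and 16% risks. These give 750 x (0.10 + 0.16) = 195 events at HR 1.65 and 1,500 x 0.10 = 150 events at HR 1.
- Assumed: one binary modifier, reference level holding 20–80% of events, patient share 10 points from event share.
- Method: normal theory with subgroup variance 4/events, 2 million draws per setting. If the gate fires, the chosen contrast is tested; otherwise the main-effects estimate is.
- Benchmark: main-effects power at HR 1 = Φ(0.5008 x √150 / 2 − 1.960) = 86.6%.

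The gate fires by chance in 15% of trials. Approximate results over all trials:

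| Contrast tested when the gate fires | Type I error at HR 1.65 | Power at HR 1 |
|---|---|---|
| Event weights | 2.5% | 87% |
| Patient-share weights | 2.6% | 86% |
| Equal weights | 2.5–3.3% | 82–87% |
| β1 literally | 3.0–4.3% | 81–84% |

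Equal and event weights give opposite verdicts at HR 1 in 0% (50/50 split), 3.1% (30/70) and 5.7% (20/80) of all trials. At the margin the figure is at most 1.2%.

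**Why event weights are safe.** With reference event share s and D events, the covariance of the event-weighted estimate with the interaction estimate is −s·4/(Ds) + (1 − s)·4/(D(1 − s)) = 0. The gate therefore carries no information about that contrast. Other weights lack this property, apart from equal weights at a 50/50 split.

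**With true heterogeneity.** Fix the event-weighted HR at 1.65 and let the two levels differ by an HR ratio of 1.5, with 60–80% of events in the reference level. Patient-share weights then reject in 1.7–4.3% of trials, depending on direction. The reason is that the targets differ. With 80% of events in the reference level and the higher HR there, the level HRs are 1.65 x 1.5^0.2 = 1.79 and 1.79/1.5 = 1.19. The equal-weighted HR is √(1.79 x 1.19) = 1.46, inside the margin, while the event-weighted HR sits on it.

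**The case against.** The strongest reply is that this is a wording gap of small consequence. It matters only if a gate fires. With no true interaction, any sensible averaged contrast stays between 2.5% and 3.3%, and event weighting stays at 2.5%. The top of the range needs a 20/80 event split, and the documents give no gender or diabetes shares. All of that stands, and it limits the size of the point. It does not supply the missing contrast.

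A reader might infer more than the documents support:

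- *That the plan intends a reference-level test.* It does not. It asks for an overall effect and presents level-specific hazard ratios in addition. The literal-β1 figures show what follows if software output is taken at face value.
- *That a Wald test on β1 is the only test named.* A log-rank test is also allowed, and the Cox model is given as an example.
- *That the interaction step by itself inflates alpha.* It does not under event weights.
- *That the rejection rates under heterogeneity are lost alpha.* Calling them errors presupposes the event-weighted estimand. They show that the estimands differ.
- *That patient-share weights are a neutral default.* They stay near 2.5% only without true heterogeneity.
- *That the site gate or the log-time option has a known error rate.* Sites number up to 50 and small ones are pooled, so the coefficient count and entry rate are unknown. The log-time model is optional, and nothing moves the margin test to it.
- *That the weights would be picked after seeing the data.* The documents do not say when.

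**Conclusion.** The point holds as a defect in a stated, mandatory rule: the primary model can change on a 0.15 test, and the quantity then compared with 1.65 is undefined. The effect on error rates is modest. The larger exposure is a change of verdict: up to 5.7% of trials at HR 1 between two defensible weightings, and a dependence on the chosen average if the effect truly varies. The figures rest on one binary modifier, the assumed event shares and a normal approximation. They cover one two-level gate such as gender x PCI, not the site gate. This should be fixed, but it does not by itself undermine the design.

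**What to change.** State in Section 10 that the sole primary margin test is the one-sided 0.025 Wald test of β1 against ln 1.65 from the main-effects Cox model, stratified by site with diabetes as a covariate, whatever the diagnostics show. Delete the rule that moves interactions into the primary model. Report interaction and log-time models as supportive, with level-specific hazard ratios.

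If the sponsor prefers to keep the rule, specify in advance:

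- the averaged contrast, its weights and its variance. Event (inverse-variance) weights keep the planned 2.5% level; any other weights define a different estimand and need a justification;
- which site x PCI x diabetes coefficients are tested jointly, and on how many degrees of freedom.

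The cost is SAP wording, with no added patients or data. The downside of the first option is that a real interaction or non-proportional hazards would be described only in supportive analyses.

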Design	
The FAME 3 trial is a multicenter, international, randomized, controlled noninferiority trial. All patients with multivessel CAD (not involving the left main) will be screened by the site's Heart Team (including but not limited to an interventional cardiologist, cardiac surgeon and research coordinator). If all agree that the patient can be treated either with FFR-guided PCI or CABG, and all inclusion criteria are met and no exclusion criteria are met, then the patient will be randomized.
 
Baseline clinical, functional, laboratory and electrocardiographic data will be obtained. Patients will receive treatment within 4 weeks of randomization. Patients randomized to CABG will receive state of the art therapy at the discretion of the local surgeon with a strong emphasis on arterial revascularization. Patients undergoing PCI will have FFR measured with a Abbott coronary pressure wire across all lesions. If the FFR is ≤ 0.80, then PCI will be performed with the Medtronic Resolute Integrity/Onyx drug-eluting stent (DES) as per usual routine. If the FFR is > 0.80 then PCI will be deferred.
 
Post procedure laboratory tests will be obtained including troponin within 12-24 hours after the procedure. Resource utilization will be obtained. All patients will receive medical therapy as per published guidelines.
 
Patients will follow-up at 1 and 6 months, and 1, 2, 3, and 5 years with an evaluation of clinical status, functional status, medications and events.
 
Core lab analyses will include formal quantitative coronary angiography (QCA) of the baseline angiograms with calculation of the Synergy between Percutaneous Coronary Intervention with Taxus and Cardiac Surgery (SYNTAX) score and Functional SYNTAX Score.

Population	A complete listing of all inclusion and exclusion criteria can be found in section 5 of the protocol.
Duration	Ten years: 5 years of enrollment and 5 years follow-up from last patient enrolled.
Primary Endpoint	Death, MI, stroke and any repeat revascularization (MACCE) will be evaluated at 1 year, where subjects contribute data from time of randomization until the occurrence of MACCE or one year follow-up,

	whichever occurs first. Subjects who die or are lost to follow up before 1 year will be censored at their last recorded activity.

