Key Secondary Endpoint	Death, MI, and stroke will be evaluated at 3 years, where subjects contribute data from time of enrollment until the occurrence of one of the above events or three year follow-up, whichever occurs first. Subjects who die or are lost to follow up before this time will be censored at their last recorded activity.
Statistics	The study will use a noninferiority design. For the primary endpoint, assuming 12% of subjects experience MACCE in the CABG arm by 1 year post randomization, given a clinically irrelevant hazard ratio of 1.65, a one-sided 2.5% significance level and 90% power to reject the null hypothesis if it is false, the sample size necessary is 645 patients per group (1290 for the entire study). To account for loss to follow-up and subject withdrawal, up to 1500 patients will be enrolled from 50 sites.
Principal Investigators	[name] (PI), [name] [name], PhD (Co-PI) and [name] [name], PhD (Co-PI)
Steering Committee	[name], [name] [name], PhD, [name] [name], PhD, [name], [name], [name], [name], [name].
Clinical Events Committee	[name], (Chair) Stanford University Medical Center ██████████, MD, Duke University Medical Center ██████████, MD, Duke University Medical Center ██████████, MD, Stanford University Medical Center
Data Safety Monitoring Board	██████████, MD, (Chair) University of California, Irvine ██████████, MD, New York Presbyterian Hospital/Weill-Cornell Medical Center ██████████, MD, UCLA Medical Center
Statistical Analysis	[name], Quantitative Sciences Unit, Stanford University Medical Center
FFR Core Lab	Stanford University Medical Center
Angiography Core Lab	Stanford University Medical Center
Economic and Quality of Life Analyses	[name], Department of Health Research and Policy Stanford University Medical Center
Clinical Research Organization	genae
Sponsor(s)	Investigator Initiated Trial, with Leland Stanford Jr. University as the official Sponsor.
Support	Study is supported through research grants by Medtronic Corp. and Abbott Vascular.

2. Summary of Investigational Plan Changes

Revision History	Effective Date
1.0	28Feb2014
2.0	15May2015
2.1	15Jun2016
3.0	27Feb2018

Version 2.0, 15May2015

Section	Change From	Change To	Rationale for Change
1.0 Protocol Summary table, Steering Committee		Added Steering Committee members [name] and [name]	Updated to include new Steering Committee members that agreed to participate after initial CIP version.

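### At equal 10% event rates, 645 per group gives about 81% power (87% at 1,500 with no loss), not 90%; Sections 1 and 10 derive the same 645 from different CABG rates

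*Combined protocol and SAP*

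**What the plan says.** Section 10 (Sample Size and Power Considerations) sets the control rate: "We assume a 10% of subjects in the CABG arm experience MACCE". For the other arm it gives an inequality, not a value: "patients in the PCI arm will not experience a higher rate than those in the CABG arm". It expresses the margin as a rate: "We would deem an increase in event rate up to and including a 16% event rate as not clinically inferior". Against a margin of 1.65 on the hazard ratio, testing one-sided at 2.5% and aiming for 90% power, it concludes: "the sample size necessary is 645 patients per group (1290 for the entire study"). The calculation is said to assume exponential event times, a Wald test and no loss to follow-up. Enrolment of up to 1,500 is there to cover loss and withdrawal, but no loss rate is given.

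Section 1 (Protocol Summary, Statistics row) repeats the margin, alpha, power and 645 per group, but starts from a different control rate: "assuming 12% of subjects experience MACCE in the CABG arm by 1 year post randomization". This is the current summary table, not the amendment log.

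The Primary Endpoint row of Section 1 limits each patient's contribution: "subjects contribute data from time of randomization until the occurrence of MACCE or one year follow-up". Section 9 has the same one-year cap.

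**The concern.** One sample size cannot follow from two control rates when the margin, alpha and power are all the same, so at least one of the two statements is wrong. Section 10's own inputs also look too low to produce enough events. With at most one year per patient and 10% of patients having an event in each arm, 1,290 patients give 129 events, which is few for a hazard ratio margin of 1.65 at 90% power.

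What is at stake is the type II error. Section 4 says the study will be considered negative if the null hypothesis is not rejected. If the real power is well below 90%, a negative result says less about PCI than the plan implies. A reader also cannot tell which CABG rate or which PCI rate the 90% rests on.

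**Working it through.** **Inputs.** Margin 1.65, one-sided alpha 0.025, power 90%, CABG rate 10% and 645 per group (Section 10); CABG rate 12% (Section 1); 1:1 allocation (Section 6); at most one year per patient (Sections 1 and 9); maximum enrolment 1,500 (Sections 1 and 10).

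**Events needed at a true hazard ratio of 1.** Schoenfeld formula, 1:1 allocation:

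d = 4(1.960 + 1.282)² / (ln 1.65)² = 4(3.242)² / (0.5008)² = 167.6, so 168 events.

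**Can 645 be reproduced?** N is d divided by the mean one-year event probability of the two arms.

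| CABG / PCI rate | Mean | N total | Per group |
|---|---|---|---|
| 10% / 10% | 0.10 | 167.6/0.10 = 1,676 | 838 |
| 12% / 12% | 0.12 | 167.6/0.12 = 1,397 | 698 |
| 10% / 16% | 0.13 | 167.6/0.13 = 1,289 | 645 |
| 12% / 16% | 0.14 | 167.6/0.14 = 1,197 | 599 |

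The stated figure matches a 13% mean rate. One route to 13% is to average the 10% CABG rate with the 16% margin rate. That would count events as if PCI were at the margin while computing power as if the arms were equal, and the two cannot both hold. This origin is an inference. The software settings are not shown, and other undocumented inputs, such as 13% in both arms, give the same number. The shortfall below does not depend on it. Freedman's formula (175 events) does not rescue the equal-rate case: it gives 875 per group at 10%/10% and 729 at 12%/12%.

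**Power delivered.** Power = Φ[(ln 1.65 − ln HR) / √(1/d_CABG + 1/d_PCI) − 1.96], with HR = ln(1 − p_PCI) / ln(1 − p_CABG).

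For 10%/10% at 1,290 patients: d = 64.5 + 64.5 = 129, SE = √(4/129) = 0.1761, 0.5008/0.1761 = 2.844, and Φ(2.844 − 1.960) = 0.812.

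For 10%/10% at 1,500 patients with no loss: d = 150, SE = √(4/150) = 0.1633, 0.5008/0.1633 = 3.067, and Φ(3.067 − 1.960) = 0.866.

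| Scenario | Power at 1,290 | Power at 1,500, no loss |
|---|---|---|
| CABG 10%, PCI 10% | 81.2% | 86.6% |
| CABG 10%, PCI 9.5% (HR 0.947) | 87.5% | 91.8% |
| CABG 12%, PCI 12% | 87.6% | 91.9% |

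A simulation of an exponential Wald test with one-year censoring (20,000 runs, 10% in both arms) gave 80.9% at 1,290 and 86.4% at 1,500.

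**PCI rate that restores 90%, with CABG at 10%.** Solving the power formula gives 9.26% at 1,290 (HR 0.92) and 9.69% at 1,500 (HR 0.97).

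**Loss to follow-up (assumed, since no rate is given).** At 10%/10%, if 5% or 10% of 1,500 contribute nothing, events fall to 142.5 or 135 and power to 84.8% or 82.9%.

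**Which control rate fits the 16% limit?** From 10%: ln(0.84)/ln(0.90) = 1.655, which agrees with 1.65. From 12%: ln(0.84)/ln(0.88) = 1.364, and a margin of 1.65 would correspond to 1 − 0.88^1.65 = 19.0%. Only 10% fits the rest of Section 10.

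**The case against.** The strongest objection is that Section 10 gives an inequality, not equal rates. A PCI rate modestly below CABG is within its wording, and at 9.26% the 1,290 patients do give 90%. That is right, and it is why the shortfall is stated as conditional on equality. But the plan names no advantage for PCI, and Section 1 hypothesises similar outcomes. A 90% claim should therefore hold at equality or name the rate it needs.

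Second, the enrolment goal is 1,500, where the shortfall at 10%/10% is only 3.4 points if nobody is lost, and there is none at 12%/12%. This also stands as arithmetic. However, the plan ties the 90% to 1,290 patients and assigns the extra patients to loss and withdrawal, and enrolment is described as up to 1,500.

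Third, the loss scenarios are pessimistic, because Section 10 keeps lost patients in the analysis until they are censored. If those lost contribute half a year on average (an assumption), power at 1,500 is about 85.7% with 5% lost and 84.9% with 10% lost. The figures for patients contributing nothing are therefore lower bounds for those loss rates.

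Finally, the 12% looks like a number left behind when Section 1 was revised. That is plausible, and it makes the correction easy, but the contradiction is in current text. The mismatch between 12% and the 16% limit follows from the same leftover and is not a separate fault.

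**Conclusion.** The concern holds. Sections 1 and 10 give the same 645 per group from 12% and 10%, and neither rate gives 90% power at that size when the arms are equal: 87.6% at 12% and 81.2% at 10%. With 10% in both arms the type II error is 18.8% at 1,290 and 13.4% at 1,500 with no loss, against a stated 10%. Reaching 90% would take about 1,676 patients, more than the enrolment cap.

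These figures rest on the plan's own exponential and Wald assumptions, one year of follow-up per patient and a true hazard ratio of 1. A PCI rate below CABG raises the power as shown. The error makes a true non-inferiority more likely to be missed. It does not affect type I error, the margin or the analysis. How 645 was obtained cannot be settled from the documents.

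**What to change.** - Use one CABG rate in both sections. Section 10 argues for 10% and its 16% limit fits only that value, so remove the 12% from Section 1.
- State the PCI rate assumed for power, and list the software inputs (rates in each arm, true hazard ratio, accrual and follow-up).
- Replace the statement of 645 per group for 90% power with what the chosen assumption delivers. At 10% in both arms: 168 events needed for 90%; about 81% power with 1,290 evaluable patients; about 87% with 1,500 and no loss.
- If a PCI rate below 10% was intended, say so and justify it: about 9.26% is needed for 90% at 1,290.

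The cost is a change of wording in Sections 1 and 10 and a less favourable stated power. Enrolment, margin, alpha and analysis stay as they are.
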